4.10.6 Determination of Intestinal Parasites

10 grams stool sample will be collected at enrolment, delivery six weeks and every six months for helminths and protozoa diagnosis. Sample will be processed with 24 hours into smears, stained appropriately and then examined under the light microscopy.

4.10.6.1 Helminths

Cestodes (tapeworms) *Taenia, Diphyllobothrium, Hymenolepis, Dipylidium, Echinococcus*, and *Spirometra* be diagnosed by collecting at least three stool samples and checking for ova and parasites. Enzyme-linked immunosorbent assay (ELISA), and polymerase chain reaction (PCR) assay may help confirm a diagnosis; depending on the species involved. *Enterobius vermicularis* associated anal pruritus will be made through microscopic identification of ova and female pinworms from perianal swabs. *Round worm; Ascaris lumbricoides* diagnosis will be made by examination of stool ova and parasite under the microscopy. Hookworms, *Ancylostoma duodenale* and *Necator americanus* diagnosis will be made by means of stool ova and parasite examination. Intestinal trematodes/*Flukes, Fasciolopsis buski, Heterophyes heterophyes, Metagonimus yokogawai*, and *Echinostoma* diagnosis is will be made by means of stool ova and parasite examination. *Microsporidia* of*Encephalitozoon hellem* and *E intestinalis species* diagnosis will be made via stool microscopy. Schistosoma ova will also be examined including the determination of the serum circulating antigens

4.10.6.2 Protozoa

Balantidium coli, Dientamoeba fragilis, Giardia lamblia, Entamoeba histolytica, Cryptosporidium including Cystoisospora belli diagnosis will be made on at least 3 different smears of stool specimens

and will be examined for trophozoites, cysts or oocytes on a microscopy and complemented by antigen detection with ELISA and or PCR.

4.10.6.3Infants stool

Infant stool collected from delivery will be diagnosed for E. coli and Cryptosporidium infections.

4.10.7 Determination of soluble biomarkers of inflammation and immune activation

Several biomarker profiles association with different comorbidities may become a power tool for individualised treatment and care.

4.10.7.1 Markers of inflammation

Hs CRP including inflammatory cytokinesIL-6, IL-10 and IL-17 will be determined.

4.10.7.2 Markers of immune activation

Plasma INF γ and interferon gamma inducing protein 10 (IP 10) (CXCL10) chemokine whilst in breastmilk RANTES (CCL5) and MIP-1 β (CCL4) chemokine will be assayed. For mothers with acute HIV infection H β D-2 ,IL-10, IL-12, IL-15, IL-17, IL12p70 determination from cervico-vaginal lavage and plasma IL-7.

4.10.7.3 Markers of Microbial translocation in coinfections

Lipopolysaccharide, soluble (s)CD14, endogenous endotoxin core antibody (EndoCAb) and bacterial 16S DNA complemented by marker of enterocyte damage, intestinal fatty acid binding protein (I-FABP) will be determined.

4.10.7.4 Markers of Monocyte and macrophage activation

SCD14, sCD163, sCD40L and IL6 will be determined. Markers of tissue fibrosis and coagulation associated with CVD related comorbidities as fibrinogen, D-dimer, a fibrin degradation product associated with endothelial dysfunction and hyaluronic acid biomarker of tissue fibrosis will be determined.

4.10.7.5Cytokine level Determination, Flow Cytometry Method

IL-2,4,6 10, TNF IFN and IL17A will be determined in a single sample (50 μ L) using the Becton, Dickinson (B cytometric Bead Array (CBA) human Th1/Th2/Th17 cytokine kit, catalogue number 560484 in either EDTA plasma or serum according to the manufacturer's instructions.

4.10.8 HIV Diagnosis

Qualitative rapid immunochromatographic assays, SD Bioline HIV-1/2 3.0 (Standard Diagnostics Inc., Kyonggi-do, South Korea) and Abbott'sDetermine[®]HIV-1/2will be used to detect HIV-1/-2

antibodies in mothers venipuncture whole blood specimens. Western blot test will be used as a tie breaker for any indeterminate test results.

4.10.9 HIV-1 RNA Load Determination

Maternal and infant plasma samples were quantified for HIV-1 RNA load using an automated TaqMan Roche Amplicor 1.5 Monitor Test (Cobas AmpliPrep/Cobas TaqMan, Roche Diagnostics, Branchburg NJ), according to the manufacturer's instructions. The detection level is 40 copies/mL.

4.10.10 Infants' Qualitative HIV-1 DNA PCR Test

Detection of infants' HIV-1 infection will be determined using a qualitative 1.5 Roche Amplicor HIV-1 DNA PCR kit (Roche Diagnostics Incorporation, Branchburg, New Jersey). This qualitative HIV-1 proviral DNA PCR tests will be done on all HIV exposed infants 'plasma samples/from birth up to 15 months past partum.

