3.1 Main Objective

This study aims to establish a birth cohort to investigate the role of HIV and comorbidities on vertical HIV transmission, immune development and disease progression in children 0-2 years, HEU, HEI and HUU as the control group.

Objectives

A. All Mothers Regardless of HIV Status

- To determine the prevalence and incidence of coinfections (intestinal parasitic infections, HBV, HCV, CMV) malnutrition and non-communicable diseases (NCDs) (gestational diabetes mellitus, hypertensive disorders and CVD) risk factors over 24 months and relate all these comorbidities to:
 - a. Pregnancy outcome, infant growth, development, morbidity and mortality
 - b. Biomarkers of inflammation and immune activations

Infants

- 2. To determine vertically transmitted infections and incidence non-communicable diseases among infants.
- 3. To determine clinical and immunological profiles of HEI, HEU and HUU infants.

B. HIV+ Mothers: Chronic HIV infections

- 1. To determine vertical transmission rates of mothers with acute and chronic HIV infection on option B+
- 2. Determine any association(s) between different option B+ drug regimens, adverse pregnancy outcome, viral load suppression and CD4/CD8 counts on mothers and their infants

C. HIV+ Mothers; Acute HIV infections,

- 1. To determine the incidence of HIV in the postpartum period over the 2 years
- 2. To determine the viral set points, HIV suppression trends and biomarkers of immune activation
- 3. To determine the HIV and host genetic diversity and possible transmission linkages

Infants

To characterise natural killer cell phenotype and function longitudinally from cord blood at birth up to 2 years and relate to infant HIV acquisition , morbidity and mortality

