4.9 Infants Procedures

From delivery infections, immunological profiles, co-infections patterns and trends, mortality will be determined and , feeding practices development , responses to standard vaccines, general health will be assessed. Types of specimen required and the test to be assayed are shown in **Tables 3 and 4**.

		Specimen Required							
Visits	Baby Status	Blood*	Stool**	Urine***	PBMCs****	1			
1	HIV+								
	HIV-								
2	HIV+								
	HIV-								
3	HIV+								
	HIV-								
4	HIV+								
	HIV-								
5	HIV+								
	HIV-								
6	HIV+								
	HIV-								
7	HIV+								
	HIV-								
8	HIV+								
	HIV-								
9	HIV+								
	HIV-								
10	HIV+								
	HIV-								
11	HIV+								
	HIV-								

Table 3: Types and total Volumes of Inf	fant Specimen Required
---	------------------------

*Generally blood samples will be tested for trend in immune profiles and coinfections.

**Stool samples will be tested for intestinal parasites

^{***} Urine for urinalysis

^{****}PBMC of infants born from mothers with acute HIV infection for NK cell phenotyping

Procedure	Specimen	1	2	3	4	5	6	7	8	9	10	
/Test	Required	Delivery	7-10 Day	6 wks	10 wks	14 wks	24 wks	36 wks	48 wks	72 wks	96 wks	
	(volume)		рр	pp V	рр	рр	рр	рр	рр	рр	рр	
CMV / HBV/ HCV	Sesement(1m)L)	• 🖌 (¥	Ť							~	1
HIV testing/all exposed infants	Plasma (2 mL)	~	1	1	~	1	1	1	1	1	1	
Parasites	Stool (5 grams)	1	1	~	1	1	1	1	1	1	1	
FBC/Differentials		~		✓		✓			1		✓	
Markers of immune activation, cytokines levels and trends	Blood,	1	1	1	1	1	1	1	1	*	1	
Urine dip stick	Urine (5 ml)		1						1		1	
Biochemistry	ALT, AST, albumin,		1	1		1			1		1	
	Sugar		1	✓		✓			1		✓	
			PMBC for int	fants born f	rom Mothers	with acute H	IV infections					
		HE	Infants only o	on First HI	V positive sar	nple, thereaft	er every 3 mor	nths				
T cell profile	Whole blood		1	1	~	~	1	~	1	~	1	
HIV RNA load*	Whole blood											1
HIV genetic diversity for Transmission	Whole blood										V]
linkages**												

Table 4: Type, Volume, intervals of collection and Purpose of Infant Specimens Required

All the tests will be done locally except for transmission linkages assay and NK cell phenotyping that will be done in South Africa.

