4.10.24 Research Outcomes

- Characterisation of comorbidities of HIV negative and HIV positive mothers
- Immune activation profiles for different comorbidities
- HIV vertical transmission rate in the era of option B+ among mothers with chronic HIV infection
- HIV incidence and postpartum vertical transmission among mother with acute HIV infection
- Transmission linkages of acute HIV infection

Research outcomes will entail improved knowledge of HEU infants immunological abnormalities and genetics resulting in their better clinical management. There will also be technology transfer in

molecular biology and genetics techniques through the establishment of research networks both locally and internationally. The project will generate a critical mass of local professions with diverse expertise as they attain higher degrees, MPhils and PhDs from sub-studies. At least ten (10) papers will be published from the parent study material.

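### Infant HIV status is to be set by a proviral DNA PCR on plasma; target and specimen do not match, so infected infants could be missed

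*Protocol*

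**What the plan says.** Protocol section 4.10.10 names the diagnostic test: "Detection of infants' HIV-1 infection will be determined using a qualitative 1.5 Roche Amplicor HIV-1 DNA PCR kit". It goes on: "This qualitative HIV-1 proviral DNA PCR tests will be done on all HIV exposed infants", and gives specimen and window as "plasma samples/from birth up to 15 months past partum". In section 4.9, the Table 4 row "HIV testing/all exposed infants" lists 2 mL of plasma and is ticked at all ten infant visits, from delivery to 96 weeks.

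Two other HIV assays are described.
- Section 4.10.8 gives the rapid tests, which detect "antibodies in mothers venipuncture whole blood specimens". Infants are not mentioned.
- Section 4.10.9 states "Maternal and infant plasma samples were quantified for HIV-1 RNA load", and section 4.10.12 also uses plasma for viral load. Tables 2 and 4, however, list whole blood for RNA load. In Table 4 the infant RNA load stands below a heading that confines it to infants from their first HIV-positive sample onward.

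Infant status feeds an objective in section 3.1, "To determine clinical and immunological profiles of HEI, HEU and HUU infants", and an outcome in section 4.10.24, "HIV vertical transmission rate in the era of option B+ among mothers with chronic HIV infection".

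**The concern.** Provirus lies inside cells, and plasma is the cell-free fraction. A test for the first run on the second looks for its target where little or none is expected. The mismatch follows from the protocol's own terms and needs no outside source.

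At stake is the test that separates HEI from HEU. A missed infection is not a neutral loss: the infant is counted as uninfected. The vertical transmission rate can then only move down, and the HEI group, already small under effective prophylaxis, loses members. If only plasma or serum has been kept, the error may not be correctable at analysis.

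**Working it through.** **Step 1. Specimens side by side.**

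| Infant test | Methods text | Table 4 |
|---|---|---|
| Proviral DNA PCR (diagnosis) | plasma (4.10.10) | plasma, 2 mL |
| HIV RNA load | plasma (4.10.9, 4.10.12) | whole blood |
| Antibody test | mothers only (4.10.8) | none named |
| Testing at 72 and 96 weeks | no assay named | plasma, 2 mL |

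For the diagnostic test, text and table agree with each other but not with the target. For RNA load, they disagree with each other.

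**Step 2. Would anything else in the protocol find a missed infant?**
- RNA load: no, because entry requires a positive sample first.
- Antibody testing: not described for infants.
- Late visits: 72 weeks is 72 × 7 / 30.4375 = 16.6 months and 96 weeks is 22.1 months. Both fall after the 15-month PCR window, and no assay is named for them. Even with a suitable assay, infants who died or were lost earlier would stay misclassified.
- Re-testing of stored cells: not assured. Section 4.10.1 describes keeping the supernatant of clotted samples. PBMCs are described for infants of mothers with acute infection (Table 3 footnote, Table 4, section 4.10.17).

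**Step 3. Size.** The protocol states no figure to reproduce. Inputs for illustration:
- N = 600 exposed infants, one for each HIV-positive mother (4.10.18), before losses.
- True rate p = 1%, the background figure in section 1.0, not a design assumption.
- Specificity 100% (assumption).
- Overall sensitivity s after all repeat tests: not given, so a range is assumed.

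Infected = N × p = 600 × 0.01 = 6. Observed rate = p × s. Missed = N × p × (1 − s). HEU contamination = missed / (N − detected).

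| s (assumed) | Detected | Missed, classed HEU | Observed rate | HEU contamination |
|---|---|---|---|---|
| 90% | 5.4 | 0.6 | 0.90% | 0.6/594.6 = 0.10% |
| 70% | 4.2 | 1.8 | 0.70% | 1.8/595.8 = 0.30% |
| 50% | 3.0 | 3.0 | 0.50% | 3.0/597.0 = 0.50% |
| 0% (bound) | 0 | 6.0 | 0% | 6.0/600 = 1.00% |

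Each missed infant lowers the rate by one sixth. The HEI group loses the fraction 1 − s, while the HEU group never takes in more than 1%.

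**Step 4. Repeat testing.** Eight of the ten visits fall by 48 weeks (11.0 months), inside the PCR window. If s were 50% for each single test and misses were independent, an infant infected from the start would be missed at all eight with probability 0.5^8 = 0.0039, about 0.4%.

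**The case against.** The strongest reply is that this is loose labelling and not a laboratory plan. Table 2 lists plasma for the full blood count, which cannot be literal, and section 4.10.2 corrects it to peripheral blood in an EDTA tube. Table 2 lists plasma for maternal HIV testing, where section 4.10.8 uses whole blood. Both tables list whole blood for RNA load, where the text uses plasma. Section 4.10.17.1 extracts RNA for env sequencing from plasma, where Table 2 lists whole blood for viral genetics. The sentence in 4.10.10 also has a stray slash that may mark a dropped alternative, and the kit's own instructions, not shown here, may settle the specimen.

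Much of this stands. Table 4 is weak corroboration, and it cannot be said that the protocol keeps blood fractions straight everywhere else. But in those examples a methods section names the fraction to be tested and so overrides the table. For the infant PCR, the methods section itself says plasma. Staff following either place would prepare plasma.

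The second reply concerns size, and it also stands in part. A reader might infer from the 50% row that half of the infections will be missed. The documents do not support that: no sensitivity is given, and testing is repeated. Repeat testing is only a partial defence, because a specimen with little target would tend to fail repeatedly in the same infant, so the independence behind the 0.4% is doubtful. A reader might also take the 3% in section 4.10.18 as a transmission rate, giving 18 of 600. That 3% is an incidence assumption tied to the few expected acute infections and does not apply to all 600 infants.

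**Conclusion.** The point holds as a mismatch between assay and specimen in the test that defines infant HIV status. It is stated in the methods section, repeated in Table 4 and corrected nowhere. Followed literally, it risks false negatives, with a known direction: a lower vertical transmission rate and a depleted HEI group.

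The size cannot be derived from the documents. With 600 exposed infants, a true rate of 1%, perfect specificity and an assumed overall sensitivity of 90% to 50%, the rate would read 0.9% to 0.5%. A reader might infer that HEU morbidity would be materially inflated. The documents do not support that: even if every infection were missed, contamination would be about 1% at a 1% true rate. Nor do they show that the laboratory would in fact test plasma, only that the protocol tells it to.

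**What to change.** In section 4.10.10 and the Table 4 row for exposed-infant HIV testing, name a cell-containing specimen (whole blood or PBMC) for the DNA PCR. If plasma is kept, state an RNA assay as the diagnostic test instead. Make both places agree.

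In the same edit:
- reconcile the RNA-load specimen, which is plasma in sections 4.10.9 and 4.10.12 but whole blood in Tables 2 and 4;
- name the infant assay used at 72 and 96 weeks, after the 15-month PCR window.

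The cost is mainly wording. Infant blood is already drawn at these visits, and neither the sample size nor the analysis changes. If a cell-containing specimen is chosen, sample handling in section 4.10.1 must provide for keeping it. The change should be made before infant samples are processed, while the cells are still available.

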4.10.11 CD4 cell counts enumeration

Absolute and percentage CD4⁺ T lymphocytes will be enumerated for all HIV positive mothers and infants using a Partec Cyflow counter (Cyflow, Partec, Munster, Germany) within 6 hours of blood collection.

4.10.12 Viral load Determination

Maternal and infant plasma viral load will be determined using automated Roche AmpliPrep COBAS AMPLICOR HIV-1 Monitor (Version 1.5) Ultrasensitive Assay according to the manufacture's instruction. All unsuppressed viral load based on a threshold of \geq 1000 copies/mL will be re-run after 3 months.

4.10.13 Markers of immune activation and senescence at enrolment and exit whole blood sample

Determine maternal activation markers, profiling by flow cytometry.CD38 on both CD4⁺ and CD8⁺ T cells. Senescence marker: CD28-CD57+ will be determined.

4.10.14 NK cell phenotypic and functional analysis

Phenotype (CD56+ dim and bright) and function on PBMCs.

4.10.15 Maternal MUAC Measurements

MUAC will be used as an indicator or predictor of nutritional outcomes. The subject's left arm should be bent at the elbow at a 90 degree angle, with the upper arm held parallel to the side of the body. Measure the mid-point distance between the bony protrusion on the shoulder and the point of the elbow will be measured. Maternal MUAC cutoffs of <22 cm to \leq 24 cm relative to the median of the sample will be used with the following assumption that;

- 1. If MUAC is <23.5 cm, BMI is likely to be <20 kg/m²
- 2. If MUAC is >32.0 cm, BMI is likely to be >30 kg/ m^2

4.10.15.1 Infant Measurements

Among children 6-60 months old assessment for acute malnutrition will be done using the 2009,

WHO and UNICEF recommendation of a MUAC cut off value of <11.5 cm

4.10.16 Determination of Hypertensive Disorders

Any one of the following will be enough to make a diagnosis of hypertension in pregnancy;

4.10.16.1 Chronic hypertension

- Preexisting hypertension: A woman diagnosed of hypertension either before she fell pregnant who may be already on treatment or first diagnosed after 20 weeks gestation and persisting after 12 weeks postpartum
- A woman with a blood pressure greater than or equal to 140/90mmHg on at least 2 separate occasions 4hours apart, anytime during the pregnancy. An Obstetrician will diagnose the following complications:

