1.8 Hypertensive Disorders

Hypertensive disorders during pregnancy represent the major cause of maternal morbidity with chronic hypertension occurring in up to 5% of pregnant womenworldwide¹⁸⁸. Mild to moderate hypertension in pregnancy is defined as systolic blood pressure of 140-159 mmHg or diastolic blood pressure of 90-109 mmHg. Hypertension during pregnancy is classified into three main categories: chronic hypertension, gestational hypertension, and preeclampsia (high blood pressure and proteinuria) with or without pre-existing hypertension. The occurrence of postpartum depression and anxiety is higher in pre-eclamptic women ¹⁸⁸. Chronic hypertension is defined as blood pressure >140/90 mm Hg that either precedes pregnancy or develops before 20 weeks gestation usually also persists beyond 42 days postpartum. Chronic hypertension is significantly higher among obese women ¹⁸⁹.Hypertension during pregnancy is more likely in women with high baseline systolic blood pressure and those with higher MUAC 190. Diet has been suggested to play a role in preeclampsia.Maternal serum concentration of the soluble receptor-1 of tumor necrosis factor-alpha (TNF-R1) a predictor of development of pre-eclampsia. Oxidative stress and endothelial cell dysfunction of the placenta have been implicated in the development of hypertension during pregnancy and vitamin intake can reduce oxidative stress and improve endothelial function ^{191;192}.Endothelial dysfunction biomarkers include VonWillebrand factor (vWF), platelet derived micro particles (PMPs), and endothelin-1 that are easily analysed by ELISA. Other serum/plasma biomarkers associated with increased risk of hypertensive disorders of pregnancy that correlate with adverse pregnancy outcomes include soluble corin, vascular endothelial growth factor, matrix metalloproteinase-1 and tissue inhibitor of metalloproteinase-1 (TIMP-1). Haemolysis, elevated liver enzymes and low platelet count (HELLP) syndrome is a risk factor for preeclampsia. HELLP is a lifethreatening obstetric complication usually beginning during the third trimester. It is characterized by

15

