2.0 Research Questions

- 1. Is the increased morbidity and mortality of HEU infants associated with increased exposure to maternal HIV load, other maternal co-infections (HBV, HCV, CMV, intestinal parasites) and how do these affect pregnant outcome and child growth and development?
- 2. Is the incidence of comorbidities, anaemia, diabetes, malnutrition and hypertensive disorders similar between HIV positive and HIV negative pregnant women and how do these affect pregnant outcome and child growth and development?
- 3. Is there a difference in biomarkers of inflammation and immune activation among mothers (HIV+/HIV-) and their (HUU/HEU/HEI) infants with different comorbidities?

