4.4 Inclusion Criteria

- Pregnant woman 18 years of age and above at 28-36 weeks gestation. The date of the last menstrual period (LMP) will be used to estimate gestational age.
- Planning to deliver at the study sites
- Able to give informed consent
 - Willing to be followed together with her baby from delivery up to two years
 - Willing to provide the required specimens

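### Section 4.10.16.1 would label hypertension first arising in late pregnancy as chronic, which conflicts with Section 1.8, and new-onset hypertension has no category of its own

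*Protocol*

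**What the plan says.** Section 4.10.16 opens with a general rule: "Any one of the following will be enough to make a diagnosis of hypertension in pregnancy". Four sub-headings follow: chronic hypertension, increased chance of pre-eclampsia, eclampsia and HELLP syndrome.

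The chronic sub-heading (4.10.16.1) has two bullets. The first, labelled as pre-existing hypertension, takes women diagnosed before pregnancy and women "first diagnosed after 20 weeks gestation and persisting after 12 weeks postpartum". The second, which has no label of its own, reads "A woman with a blood pressure greater than or equal to 140/90mmHg on at least 2 separate occasions 4hours apart, anytime during the pregnancy". It sets no onset limit and no persistence condition.

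Section 1.8 is the only place where the protocol sets out its categories: "chronic hypertension, gestational hypertension, and preeclampsia (high blood pressure and proteinuria) with or without pre-existing hypertension". It then says: "Chronic hypertension is defined as blood pressure >140/90 mm Hg that either precedes pregnancy or develops before 20 weeks gestation". It adds that such hypertension usually lasts beyond 42 days after delivery.

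Eligibility (Section 4.4) is "Pregnant woman 18 years of age and above at 28-36 weeks gestation". Research question 2 (Section 2.0) asks: "Is the incidence of comorbidities, anaemia, diabetes, malnutrition and hypertensive disorders similar between HIV positive and HIV negative pregnant women". The objectives in Section 3.1 likewise ask for prevalence and incidence, with hypertensive disorders named as one group.

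Two other definitions matter here. Section 4.10.3.5 plans to measure 1,25(OH)2 vitamin D but gives its deficiency cut-off, below 25 nmol/L, for 25-OH vitamin D. Section 4.10.16.4 lists a platelet count below 100,000/µL as an element of HELLP, as does Section 1.8, and then defines a HELLP Class 3 of 100,000-150,000/µL.

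**The concern.** Section 4.10.16 is the operative rule by which women will be classified. Followed as printed, it puts new hypertension of late pregnancy under the chronic heading. Section 1.8 would not call that disease chronic, and Section 4.10.16 offers no other heading for new hypertension without complications.

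This matters because the research question and objectives ask about incidence as well as prevalence. Incidence depends on separating disease already present from disease that arises under observation. If the chronic label holds both, a report of chronic hypertension by HIV status mixes prevalent and incident cases, and any separation built on that label inherits the mixture.

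**Working it through.** The protocol states no figure on this point that could be reproduced, so the check is a comparison of definitions, with simple arithmetic on the limits.

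**Enrolment against the 20-week limit.** Inputs: 28-36 weeks (Section 4.4) and 20 weeks (Sections 1.8 and 4.10.16.1). 28 − 20 = 8 and 36 − 20 = 16, so enrolment falls 8 to 16 weeks after the limit. No blood pressure taken by the study in pregnancy can show onset before 20 weeks. That information has to come from records.

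**The two definitions on four illustrative cases.**

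1. *Normal until 30 weeks, two qualifying readings then, resolved by 6 weeks after delivery.* Section 4.10.16.1 as printed: under the chronic heading through the second bullet. Section 1.8: not chronic. Section 4.10.16 has no gestational heading to receive her.
2. *Onset after 20 weeks, first diagnosed at 30 weeks, persisting past 12 weeks postpartum.* Section 4.10.16.1: chronic, and pre-existing under the first bullet. Section 1.8: not chronic.
3. *First diagnosed at 16 weeks.* Section 1.8: chronic. The first bullet of 4.10.16.1 does not cover her, since diagnosis was neither before pregnancy nor after 20 weeks. Only the second bullet can bring her in.
4. *Onset at 16 weeks, undetected until enrolment, persisting past 12 weeks postpartum.* Chronic under both sections.

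**Does the conflict depend on the heading?** Suppose the second bullet is really the general criterion, placed under the wrong heading. Case 1 then becomes hypertension in pregnancy without a subtype, and the mislabelling goes. Case 2 still conflicts through the first bullet. Case 3 now has no place in the chronic definition, although Section 1.8 includes it. Case 4 still agrees. The passages therefore remain unreconciled on either reading. The cases show where the texts part; they say nothing about how many women are affected.

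**Secondary definitions.** The vitamin D analyte to be measured and the analyte of the cut-off differ, and no 25-OH assay is stated, so the deficiency category cannot be assigned from the planned measurement. For HELLP, the ranges below 100,000 and 100,000-150,000 share no value, so a woman who meets the platelet element cannot be in Class 3.

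**The case against.** The best defence is structural. The general rule at the head of Section 4.10.16 governs the list, the first bullet carries its own pre-existing label, and the second carries none. The section then moves on to complications that an obstetrician will diagnose. On that reading the second bullet simply detects hypertension in pregnancy and calls nobody chronic. This reading is open and would remove the most visible mislabelling, but the first bullet would still disagree with Section 1.8 in both directions.

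A reader might infer that the two sections set contrary onset limits. The documents do not support that. Section 4.10.16.1 speaks of when hypertension is first diagnosed, Section 1.8 of when it develops, and case 4 satisfies both. Since women are enrolled at 28-36 weeks, a pressure from before 20 weeks may not exist, and persistence after delivery can reasonably be used as evidence of earlier disease. What stands is narrower: the first bullet also admits true late-onset disease that persists.

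A reader might also infer that the 12-week persistence mark cannot be assessed because no visit falls on it. That is no defect: a 14-week visit with a physical examination is already scheduled (Section 4.8).

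It is fair to add that Section 1.8 is background text, and that no objective or endpoint names a hypertension subtype, vitamin D deficiency or HELLP class. These facts limit the consequence but do not make the definitions agree. On HELLP, the protocol does not say that all three elements must be present together, so Class 3 is not shown to be empty, only incompatible with the platelet element. The Class 1 sign may be a misprint, and nothing here rests on it.

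**Conclusion.** The point holds as a contradiction in an operative definition that should be corrected. As printed, women first hypertensive in late pregnancy are labelled chronic, contrary to Section 1.8, and new-onset hypertension has no category. If the second bullet is taken as the general criterion, the first bullet still admits late-onset disease that persists and still leaves out hypertension first diagnosed between conception and 20 weeks.

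The reach is limited. A reader might infer that the overall figures for hypertension in pregnancy are compromised; they are not, because any listed criterion suffices for that diagnosis. What is affected is the subtype labels and any split of prevalent from incident disease that relies on them. The number of women involved cannot be stated, because the protocol gives no frequency of hypertension by time of onset for this cohort. Dated pressures and records may allow later reclassification where they exist.

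The conclusion assumes that classification follows the protocol text and that no other document overrides it. The vitamin D and HELLP mismatches are real but secondary.

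**What to change.** Reconcile Sections 4.10.16 and 4.10.16.1 with Section 1.8:

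- Place the any-time blood pressure criterion under the general definition that opens Section 4.10.16.
- Give new-onset hypertension its own category.
- Separate it from pre-existing disease by one stated onset or diagnosis limit, saying which of the two is meant, and by one persistence mark assessed at a visit already scheduled. Moving the second bullet alone is not enough.
- Take onset before enrolment from the obstetrical records already collected under Section 4.8, and record onset as unknown where those records do not reach back far enough.

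Which clinical definition applies is for the investigators to choose.

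In Section 4.10.3.5, make the assay and the cut-off refer to the same vitamin D metabolite, or drop the deficiency category. In Section 4.10.16.4, reconcile Class 3 with the platelet element given there and in Section 1.8.

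The cost is protocol and case report form wording. Blood pressure readings, visits and record collection stay as planned. For vitamin D the cost is either naming the matching assay on serum already drawn or deleting the category. Some women will remain of unknown onset, which wording cannot cure but the analysis can then show openly.
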